- Participant should be encouraged by the site to have nasal swabs and saliva samples (if feasible) collected from participants (by qualified study site staff/HCP) as indicated in the Schedule of Activities. If the participant is unable or unwilling to have all samples collected as requested, the participant should still complete the other COVID-19 assessments, including the visit at COVID-19 Day 29.

- e. Participants should undertake the COVID-19 procedures until 14 days after signs or symptom onset/positive molecular test from outside the study (COVID-19 Day 15) or until resolution of the COVID-19 episode, whichever comes last. Resolution of a COVID-19 episode is defined as having 1 SARS-CoV-2 negative nasal swab and 2 consecutive days with no COVID-19-related signs or symptoms. Once past COVID-19 Day 15, collection of nasal swab and saliva samples (if feasible) from participants should be stopped as soon as 1 nasal swab sample is SARS-CoV-2 negative, but (if still symptomatic at that time) the participant should continue completing the PROs (including SIC, body temperature, and pulse oximetry) in the eCOA until 2 consecutive days with no COVID-19-related signs or symptoms.
- f. If any of the COVID-19 visits coincide with a scheduled visit in the main SoA, combining the visits is preferred and any blood samples that are listed in both visits should only be collected once. For example: if the COVID-19 visit Day 29 falls within the main SoA Day 29 visit window, visits can be combined and the COVID-19 humoral immunity (serum) sample is not necessary, as a sample will be collected as part of the main SoA Day 29 visit.
- g. If a participant has a positive test result for SARS-CoV-2 infection and/or depending on the medical status of the participant, the participant may be requested to not visit the study site (per local or institutional regulations) but to keep the participant at home. If necessary, study-site personnel will visit the participant at home, if allowed by local regulations. Under these circumstances, the participant will be contacted by the site at least once per week to follow-up on the participant's condition and the participant's medical care provider will be notified.

The site staff or HCP visiting the participant at home will use personal protective equipment according to local regulations.

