If the participant has a SARS-CoV-2 positive nasal swab collected on COVID-19 Day 1 to 3 or from outside the study, then the participant will be asked to undertake the COVID-19 procedures until 14 days after signs or symptom onset/positive RT-PCT test from outside the study (COVID-19 Day 15, if applicable) or until **resolution of the**

COVID-19 episode, whichever comes last^a. Resolution of the COVID-19 episode is defined as having 1 SARS-CoV-2 negative nasal swab and 2 consecutive days with no COVID-19-related signs or symptoms. Once past COVID-19 Day 15, nasal swabs and saliva sample will no longer be collected from the participant as soon as 1 nasal swab is SARS-CoV-2 negative, but (if the participant is still symptomatic at that time) the participant should continue completing the PROs (including SIC, body temperature, and pulse oximetry) in the eCOA until 2 consecutive days with no COVID-19-related signs or symptoms.

Note: for participants who have signs and symptoms present at baseline (assessed pre-vaccination), only signs and symptoms that are associated with COVID-19 and that developed during the COVID-19 episode are to be taken into account.

Upon closure of the COVID-19 episode and procedures, all participants will fall back to the default Schedule of Activities (Section 1.3). If the participant experiences new signs or symptoms suggesting possible COVID-19 at a later point in time, the participant would restart the COVID-19 procedures from COVID-19 Day 1 onwards (Section 1.3.3).

All confirmed COVID-19 episodes will be communicated to the participant and to other authorities according to local regulations.

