5.8.3. COVID-19-like Signs and Symptoms

Procedures to be performed in the event a participant experiences signs or symptoms suggesting possible COVID-19 are detailed in CTP Section 1.3, Schedule of Activities and CTP Section 8.1.2, Procedures in case of COVID-19-like Signs and Symptoms.

The COVID-19-like Signs and Symptoms will be analyses for the participants with a COVID-19 infection. The presence of SARS-CoV-2 infection will be assessed at the study site by molecular testing using the nasal swab sample and also based on SARS-CoV-2 N serology results. It is defined as a SARS-CoV-2 N serology (N-ELISA) change from baseline result from negative to positive, or a positive SARS-CoV-2 PCR-status.

The analyses described in this section will be conducted on the FAS at the time of the final analysis.

The number and percentage of participants with at least one SARS-CoV-2 infection will be tabulated by vaccination schedule.

In the group of participants seronegative at baseline, the number and percentage of participants with at least one positive non-S protein ELISA (e.g., N ELISA), if available, will be tabulated by vaccination schedule.

For each participant with confirmed COVID-19 infection, a narrative will be prepared based on the visit performed 28 days after the onset of COVID-19 signs and symptoms and other selected information from the clinical database, as available:

- participant ID
- vaccination regimen
- sex, race, ethnicity, age, BMI, dates at which vaccinations were received
- pulse oximetry
- physical examination findings based on the visit performed 28 days after the onset of COVID-19 signs and symptoms
- vital signs including body temperature based on the visit performed 28 days after the onset of COVID-19 signs and symptoms
- Humoral immune responses as collected at the planned time points + those obtained from the blood sample taken on the visits performed 3 and 28 days after the onset of COVID-19 signs and symptoms. This information may be presented graphically.

For the analysis of the SIC (Patient Reported Outcomes, PRO) data, the following considerations apply:

- An “episode” is defined as a period in which any symptoms are reported on the SIC, starting from the first day on which symptoms were reported until the first day that the PRO was not completed because the symptoms had resolved (this will be indicated in the SDTM data, with reason for not completing the PRO = “Symptoms resolved” (or similar) or death)

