- A symptom (e.g. feeling generally unwell, fatigue, physical weakness, cough, etc.) is assumed to be present on each day the associated Yes/No question is answered “Yes” or the associated severity question has a rating > 0 .
- If the PRO was not completed due to the participant being too ill or due to the participant being hospitalized, the symptom will be considered present with maximum severity score. If the PRO was completed due to any other reason, no imputations will be done.

Duration of the episode will be calculated as (episode end date – episode start date) + 1. Duration of each symptom will be calculated as last date of symptom reporting – its first date + 1.

The following analyses will be conducted for confirmed SARS-CoV-2 infection cases:

- At the level of first episodes, the following statistics will be calculated: number of episodes, mean and median duration of episodes (with min, max, q1 and q3), and mean and median number of symptoms reported per episode (with min, max, q1 and q3).
- At the level of the symptoms for each first episode, the following statistics will be calculated: number of participants experiencing the symptom, mean and median duration of each symptom (with min, max, q1 and q3), median (with min, max, q1 and q3) of highest severity of each symptom, median duration of the highest severity of each symptom (with min, max, q1 and q3).
- At the level of the participants, for each episode and each symptom separately, the duration, and minimum and maximum severity scores will be tabulated (as available).

In addition, participant listings will be provided containing the SIC information for each time point. Details about these analyses will be provided in the DPS.

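### Read literally, SAP 5.8.3 ends a resolved COVID-19 symptom episode on a symptom-free day, so its duration is at least one day longer than the symptoms lasted

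*SAP*

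**What the plan says.** SAP 5.8.3 says that an episode "is defined as a period in which any symptoms are reported on the SIC". It begins with the first symptomatic day and runs "until the first day that the PRO was not completed because the symptoms had resolved". The end is found in the SDTM data from the recorded reason for non-completion: symptoms resolved (or similar), or death. Days missed because the participant was too ill or in hospital are instead counted as symptomatic at maximum severity.

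The SAP then gives two duration formulas. For the episode: "Duration of the episode will be calculated as (episode end date – episode start date) + 1". For a single symptom: "Duration of each symptom will be calculated as last date of symptom reporting – its first date + 1".

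Mean and median episode duration, with range and quartiles, are calculated for first episodes only. A participant-level tabulation covers every episode, listings show the SIC at each time point, and further detail is left to the DPS.

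The protocol uses a different notion of resolution. Section 8.1.2 states: "Resolution of the COVID-19 episode is defined as having 1 SARS-CoV-2 negative nasal swab and 2 consecutive days with no COVID-19-related signs or symptoms". Under Section 1.3.3, footnote e, a participant past COVID-19 Day 15 whose swab has turned negative but who still has symptoms goes on completing the PROs, including the SIC, "in the eCOA until 2 consecutive days with no COVID-19-related signs or symptoms". Otherwise, the Section 1.3.3 schedule asks for the daily SIC only when there are signs or symptoms. Footnote o lets a participant without symptoms complete just the surveillance symptom check.

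**The concern.** An episode described as a period of reported symptoms should end on the last day a symptom is reported. The SAP's end point is instead a day on which, by construction, no symptom is reported, and the plus 1 in the formula counts that day. The SAP never defines the episode end date separately, so two programmers could derive different durations from the same data.

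A participant with one continuous symptom would also show two different durations in the same set of outputs, one for the symptom and a longer one for the episode.

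A second problem can act in the opposite direction. The SAP rule asks for no minimum run of clear days. One gap day entered as resolved closes the episode, and symptoms that return the next day start another, which the first-episode statistics do not include.

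At stake are the prespecified mean and median episode durations, which would depend partly on when the questionnaire stopped and not only on the illness.

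**Working it through.** The documents give no episode-duration figure to reproduce, so the check is date arithmetic with the SAP's own formulas. Let S be the first symptomatic day and L the last, with S = 1 in the examples.

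**1. SIC stops the day after the last symptom.** The schedule and footnote o in protocol Section 1.3.3 permit this. The end date read literally is L + 1.

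- Symptom-based duration: L − S + 1.
- SAP episode duration: (L + 1) − S + 1 = L − S + 2.

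| Symptomatic days | SAP, literal | Excess |
|---|---|---|
| 1 | 2 | +100% |
| 3 | 4 | +33% |
| 5 | 6 | +20% |
| 7 | 8 | +14% |
| 10 | 11 | +10% |
| 14 | 15 | +7% |

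If the uncompleted day is excluded, the end date is L and the excess is zero (5 stays 5).

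**2. Still symptomatic past Day 15, SIC completed through two clear days (footnote e).** Take symptoms on Days 1 to 16. Days 17 and 18 are completed without symptoms, and Day 19 is the first uncompleted day.

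- Symptom-based: 16 − 1 + 1 = 16.
- Day 19 counted: 19 − 1 + 1 = 19, an excess of 3.
- Day 19 excluded: 18 − 1 + 1 = 18, an excess of 2.

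Excluding the uncompleted day does not remove the excess here, because completed clear days do not end an SAP episode.

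**3. Intermittent symptoms.** Symptoms on Days 1 to 4, none on Day 5, symptoms on Days 6 to 9, none afterwards.

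- Day 5 entered as resolved: first episode 5 − 1 + 1 = 5 days; second episode 10 − 6 + 1 = 5 days. Only the first enters the summary statistics.
- Day 5 completed with no symptoms: one episode, 10 − 1 + 1 = 10 days, with nothing split.
- Ending on the last symptomatic day before two consecutive clear days: 9 − 1 + 1 = 9 days.

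**The case against.** The best defence is that the end date is merely unclear. The word until can be read as excluding the uncompleted day, the SAP's opening description supports that reading, and the DPS may settle it. This stands in part. The one-day excess depends on the literal reading, so it cannot be said that every resolved episode is overstated whatever the reading. But the exclusive reading gives zero excess only if the SIC stops on the first clear day. It still leaves 2 days in the past-Day-15 case.

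A reader might infer that any missed diary day ends an episode. It does not: the recorded reason must be that symptoms resolved, or death.

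A reader might also infer much larger errors, for example that symptoms on Days 1 to 4 would be reported as 7 days (two clear days completed first) or 16 days (SIC kept to Day 15). The documents do not support this. The instruction to continue through two clear days is limited to participants still symptomatic past Day 15, and before that a symptom-free participant needs only the symptom check.

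It is also fair to say that the protocol's resolution rule governs when COVID-19 procedures close, not how a questionnaire episode is analysed, so the SAP need not adopt the swab criterion. Splitting is conditional: it needs a resolved entry on a gap day. Footnote o makes that plausible, but the documents do not show how often it would occur. The later episode remains in the participant-level tabulation.

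**Conclusion.** The concern holds as a defect in one derivation. Taken literally, SAP 5.8.3 adds one symptom-free day to an episode closed as resolved when the SIC stops the day after the last symptom. It adds 3 days (2 if the uncompleted day is excluded) for participants still symptomatic past Day 15 who complete the SIC through two clear days. The rule disagrees with the SAP's own opening definition and with its per-symptom duration. A gap day recorded as resolved can instead make the first episode too short: 5 days against 9 in the example.

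In absolute terms the error is small, but one day is 20% to 33% of an episode of 3 to 5 days. It would be too strong to conclude that the statistic mostly measures how long the diary was kept; it does so in part. The analysis is exploratory and descriptive, and no hypothesis, sample size or primary endpoint is affected.

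**What to change.** Define the episode end date explicitly in SAP 5.8.3:

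- It is the last day with a symptom reported, or imputed as present because the participant was too ill or hospitalised, before at least 2 consecutive symptom-free days.
- A symptom-free day is a completed SIC with no symptoms, a symptoms-resolved entry, or a negative symptom check.
- If the participant dies during the episode, it is the date of death.
- Duration stays end minus start plus 1, which then matches the per-symptom formula.

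Symptoms that return after a single clear day then belong to the same episode. The SAP should also say how a day with no record is treated, because the symptom check is due only at least twice a week and two clear days in a row may not both be recorded.

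The cost is one changed derivation, with the matching DPS text, before the final analysis. It draws on the symptom check as well as the SIC and needs no new data. Most resolved episodes would become shorter than under the literal rule, and some split episodes would be rejoined and become longer.

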5.8.4. Demographics and Baseline Characteristics

Demographic and baseline variables will be summarized by vaccination schedule and overall for the FAS. Details about demographics and baseline characteristics are provided in Section [6.4](#).

SARS-CoV-2 Serostatus at baseline will be derived from the S-ELISA, N-ELISA as well as from MSD 4, if available. Seronegative at baseline is defined as negative per S-ELISA and per N-ELISA (values \leq LLOQ) and, if available, per MSD 4plex S and MSD 4plex N (values \leq LOD or LLOQ*). Seropositive at baseline is defined as positive per S-ELISA or per N-ELISA (values $>$ LLOQ), or, if available, per MSD 4plex S or per MSD 4plex N (values $>$ LOD or LLOQ*). SARS-CoV-2 Serostatus at baseline will be assigned to ‘no baseline’ if the S-ELISA or N-ELISA results are missing. Since MSD 4 results were not available by the time of the primary analysis, and the same derivation rules will be applied for the final analysis, SARS-CoV-2 Serostatus at baseline will be derived from the S-ELISA, N-ELISA only.

5.8.5. Definition of Subgroups

Subgroups are defined in as shown in [Table 6](#).

Table 6: Definition of subgroups

Subgroup (at baseline)	Definition
Age Group	
 12-15 years (≥ 12y to < 16y) 16-17 years (≥ 16y to ≤ 17y)
BMI	
 underweight ($< 18.5 \text{ kg/m}^2$) normal ($18.5 < 25 \text{ kg/m}^2$) overweight and obese ($\geq 25 \text{ kg/m}^2$)
Race	
 Asian Black or African American White Other ('Multiple^a or 'Native Hawaiian or other Pacific Islander' or 'American Indian or Alaska Native')
Ethnicity	
 Hispanic or Latino Not Hispanic or Latino
Sex	
 Male Female
SARS-CoV-2 Serostatus	
 Positive Negative

^a If multiple race categories are indicated, the Race is recorded as 'Multiple'.

For safety and immunogenicity analyses, results will at least be analyzed by vaccination schedule and age (at baseline) group.

Safety and immunogenicity subgroup analyses will also be performed for selected summaries by sex, by SARS-CoV-2 serostatus at baseline (or in seronegative subgroup only if there are less than 5% of seropositive subjects), as well as by BMI at baseline, by race, and ethnicity for the primary endpoints. Subgroup analysis will ignore unknown, missing and not reported values, unless otherwise specified.

5.9. Planned and Interim Analyses

The following analyses are planned based on the Part 1 data:

- Regular monitoring of the safety data will be performed by IDMC, which is unblinded to the study data, based on cumulative data available in the database from approximately 6 months after start of recruitment.
- A first IDMC (unblinded) analysis of Part 1 will be performed on safety and reactogenicity data 28 days post-dose 1.
- A second IDMC (unblinded) analysis of Part 1 will be performed on safety and reactogenicity data 28 days post-dose 2.
- Selected sponsor members will also review group unblinded summaries of those two IDMC analyses, as well as of any available immunogenicity data up to 28 days post-dose 1 and up to 14 days post-dose 2.
- Interim analyses may be performed for safety and/or immunogenicity, to facilitate decision making with regards to planning of future studies or for regulatory submission purposes prior to the final analysis.

- A primary analysis of safety, reactogenicity and immunogenicity data up to 28 days post-dose 2 will be performed and the selected dose level will be determined for any future pediatric studies. The sponsor will be unblinded at the time of the primary analysis, but the blind will be maintained at a participant and study site level up to the unblinding visit.
- The final analysis will be performed when all participants have completed their last visit in Part 1 or discontinued earlier.

5.9.1. Non-binding Guidelines on Dose and Regimen Selection

Non-binding guidelines on dose and regimen selection were originally defined to determine the most appropriate dose level for Part 2 and any future pediatric studies. However, following the cancellation of Part 2, those guidelines will not be assessed in the context of this study.

Assuming a monotone dose-response on immunogenicity, the maximum dose with acceptable reactogenicity will be selected based on an assessment of the rate of local and systemic Grade 3 adverse events. The assessment of acceptability will take a non-binding dual Go/No-Go framework for each dose into account. The reactogenicity will be compared to the reactogenicity data from young-adult participants of study COV3001 and COV3009. The difference in reactogenicity is flagged as:

- acceptable, if the upper bound of the one-sided 95%-Confidence interval on the rate difference of local and systemic adverse events to the young-adults is below 20%.
- problematic, if the difference is not deemed acceptable and the lower bound of the one-sided 90%-Confidence interval on the rate differences of local and systemic adverse events to the young adults is above 10%, or if any Pyrexia event of Grade ≥ 3 has been observed on the considered dose.

Above guidelines lead under the assumption of N=50 participants per study group from COV3006 to an observed rate difference of up to $\sim 10\%$ being flagged as acceptable. A difference of $\sim 20\%$ or larger would be flagged as problematic by the considered guidelines. A problematic dose could still be considered as acceptable for continued evaluation based on clinical reasoning.

Reactogenicity is assumed to increase with increasing doses. If a low dose has been deemed as problematic, any higher dose will automatically be deemed as at least as problematic.

Assuming an underlying grade 3 event rate in the COV3001 (or COV3009) comparator group of 20%, the considered guidelines will result in the probabilities of declaring a dose as acceptable or problematic shown in [Table 7](#).

Table 7: Probability to Outcome by Event Rate

Event rate COV3006	Probability of acceptable outcome	Probability of inconclusive outcome	Probability of problematic outcome
20% ($\Delta=0\%$)	97.5%	2.4%	0.1%
30% ($\Delta=10\%$)	48.2%	44.7%	7.1%
40% ($\Delta=20\%$)	4.3%	46.2%	49.5%
50% ($\Delta=30\%$)	0.7%	8.5%	91.4%

5.9.2. Data Monitoring Committee (DMC) or Other Review Board

An Independent Data Monitoring Committee (IDMC) has been commissioned to review the safety data of this trial alongside the other COVID-19 trials. Please refer to the IDMC Charter.

6. SUPPORTING DOCUMENTATION

6.1. Appendix 1 List of Abbreviations

AE	adverse event
AESI	Adverse event of special interest
BMI	Body Mass Index
CI	confidence interval
CoV	Corona Virus
COVID-19	Corona Virus Disease 2019
CRF	case report form
CSR	Clinical Study Report
CTP	Clinical Study Protocol
DMC	Data Monitoring Committee
DPS	Data Presentation specifications
DRC	Data Review Committee
eCRF	electronic case report form
ELISA	Enzyme-linked immunosorbent assay
ELISpot	enzyme-linked immunospot
FAS	Full Analysis Set
FDA	Food and Drug Administration
FOIA	Freedom of Information Act
FU	Follow-up
GMC	Geometric mean concentration
GMR	Geometric mean titer ratio (GMT adolescents / GMT young adults)
GMT	Geometric mean titer
ICH	International Conference on Harmonization
ICS	Intracellular Cytokine Staining
IFN- γ / IFN-g	Interferon gamma
IL	Interleukin
ITT	Intent-to-Treat
IU/ml	International units per milliliter
IWRS	interactive web response system
kg	Kilogram
LLOQ	lower limit of quantification
LOD	Limit of detection
m	meter
MAAEs	Medically Attended Adverse Events
Max	Maximum
MedDRA	Medical Dictionary for Regulatory Activities
Min	Minimum
N	Number
NA	Not Applicable
PBMC	peripheral blood mononuclear cell
PD	Pharmacodynamic
PI	principal investigator
PK	pharmacokinetic(s)

PP	Per Protocol
PPI	Per Protocol Immunogenicity Set
PRO	Patient Reported Outcome
Q1	First quartile
Q3	Third quartile
RNA	Ribonucleic acid
S	Spike
SAE	serious adverse event
SAP	Statistical Analysis Plan
SARS	Severe acute respiratory syndrome
SARS-CoV-2	Severe acute respiratory syndrome coronavirus-2
SD	standard deviation
SDTM	Study Data Tabulation Model
SE	Standard error
SIC	Symptoms of Infection with COVID-19
Th1	Helper cell type 1
Th2	Helper cell type 2
TLF	Tables, Listings and Figures
TNF- α / TNF-a	Tumor necrosis factor alpha
ULOQ	Upper limit of quantification
VNA	Virus Neutralization Assay
WHO	World Health Organization

